[figure not shown]
II. Study design

This is a pilot study that will evaluate the feasibility of a home-based approach to influenza infection for households in the Seattle, WA area, utilizing an influenza self-test, followed by telehealth consultation for diagnosis and rapid home delivery of antivirals. Households with 3 or more of the same members at least 4 days per calendar week will be eligible to enroll, as long as there are at least 2 members in household eligible to take BXM. Individuals 12 years or older, weighing at least 40 kg, will eligible to take BXM, and thus, are able to enroll as drug eligible participants. Individuals that are not able to take BXM will be able to enroll in the study as drug ineligible participants. Individuals within an eligible household will be enrolled prior to or during the annual influenza season and monitored throughout the influenza season for the development of a cough or 2 or more respiratory symptoms. If a drug ineligible study participant, meaning a household member who does not meet BXM criteria, develops symptoms, they will use an influenza self-test; however, regardless of the result, they will not be able to receive BXM. Nevertheless, the drug ineligible study participant will provide one self-collected or parent/permanent legal guardian-collected nasal swab specimen that will be mailed back to the laboratory for further testing.

If a drug eligible study participant in the household develops a cough or 2 or more respiratory symptoms, he/she will use a prepositioned influenza self-test kit as soon as possible. Additionally, the individual will connect with a healthcare provider through the 98point6 app to

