review the participant’s medical information and provide an influenza diagnosis based on clinical judgement. If probable influenza is diagnosed, the 98point6 provider will confirm that antiviral treatment is appropriate. If appropriate, drug eligible study participant will subsequently receive a single dose of BXM delivered to their household via rapid delivery service for therapy initiation within 48 hours of symptom onset. Concurrently, the ill individual will collect a Study Day 0 nasal swab sample that will be mailed back to the laboratory for further testing. Additional nasal swabs will be collected at Study Day 2-3 and Study Day 5-7. If influenza is not diagnosed, the ill individual will provide one self-collected or parent/permanent legal guardian-collected nasal swab specimen that will be mailed back to the laboratory for further testing, and the household will remain enrolled and all study participants in the household will continue to self-monitor for presence of symptoms. Once an eligible study participant receives BXM, no additional household members will be eligible to receive BXM; the household will be able to continue monitoring for onset of symptoms, as well as self-testing and swabbing when symptoms develops, but the household will no longer be able to receive BXM delivery.

Figure 1. Study schema

Symptom Table

Feeling Feverish	Muscle or Body Aches
Headache	Rash
Sore Throat or Itchy/Scratchy Nose	Runny/stuffy nose
Feeling More Tired Than Usual	Muscle or body aches
Nausea or Vomiting	Increased trouble with breathing
Ear Pain or Ear Discharge	Diarrhea

The study is being conducted in the Seattle, WA area over one influenza season. The goal is to have 250 households comply with full study procedures. Of these, 25% are estimated to have an individual in the household diagnosed with influenza based on estimates from previous household studies.^{23, 28-29}

A table for influenza attack rates by household size is provided below.

Household attack rate	Total households enrolled	Primary cases	Secondary cases (mean household size 5)	Secondary cases (mean household size 4)	Secondary cases (mean household size 3)
25%	250	63	45-96	34-72	23-48
20%	250	50	36-76	27-57	18-38
10%	250	25	18-38	14-29	9-19
Mean household size includes case.					
Secondary attack rate 18-38%, secondary cases presented as a range based on these high and low bounds. ³⁰⁻³²					

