A list of serious adverse events will be presented by shelter and by treatment v. intervention period. As defined in the study protocol, serious adverse events include death, a life-threatening reaction to the study drug (or placebo) or other study procedure, hospitalization, or significant or persistent disability or impairment. The incidence of SAE's (events/person-days of follow-up) will be presented both (1) overall and (2) by case v. non-cases. We will test for a difference in SAE rate between the two study periods (intervention v. control) using an exact Poisson test in R.

Baloxavir-resistant influenza transmission

Evidence of a strong intervention effect causing incidence of baloxavir-resistant influenza strains will be evaluated using linear mixed effects logistic regression. The unit of analysis will be influenza-positive tests, and the outcome will be binary: baloxavir-resistant or not baloxavir-resistant.

B5. Power sample size

Table 1. Sample size calculations: Number of clusters needed per arm for two-group cluster-randomized trial - Household intervention study

Effect size (% reduction in flu incidence)			
Power	0.30	0.40	0.50
0.80	57	84	129
0.90	76	112	172

All calculations above assume an ICC of 0.29, anticipated average (or actual) cluster size of 4, and a 15% transmission rate for flu.

Based on these calculations, an arm size of 250 households should be sufficient to detect a 30% reduction in flu incidence at 90% power.

B6. Endpoint Analyses

Primary Analysis

[figure not shown]
Question: Does this home-based self-test diagnostic tool and rapid treatment intervention lead to a large percentage of influenza-positive individuals initiating antiviral therapy within 48 hours of symptom onset?

Endpoint: Cumulative incidence of influenza virus infection

Measure of Association:
Cumulative Incidence (Attack Rate, Incidence Proportion)

$$\text{Cumulative Incidence} = \frac{\text{Number of participants that successfully initiate antiviral therapy within 48 hours of symptom onset (among participants who have a cough and self-test positive for influenza) during the October 2019-May 2020 influenza season}}{\text{Number of influenza-free participants at risk at } t_0 \text{ (baseline)}}$$

Relevant DAG

Exposure:

Exposed (Treatment) = Participants who develop cough and self-test positive
Unexposed (No treatment) = Participants who develop cough but self-test negative

Outcome:

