Success = Participant initiated on antiviral therapy within 48 hours of symptom onset
Failure = Participant is not initiated on antiviral therapy (**more than 48 hours** after symptom onset *or* participant **never** initiates antiviral therapy)

Table 1. Estimated secondary attack rates for planned 2019-2020 study aim on household transmission dynamics.

The study is being conducted in the Seattle, WA area over one influenza season. The goal is to enroll at least 250 (up to 1,000) households. Of these, 25% are estimated to have an individual in the household diagnosed with influenza based on estimates from previous household studies.^{23, 28-29}

A table for influenza attack rates by household size is provided below.

Household attack rate	Total households enrolled	Primary cases	Secondary cases (mean household size 5)	Secondary cases (mean household size 4)	Secondary cases (mean household size 3)
25%	250	63	45-96	34-72	23-48

20%	250	50	36-76	27-57	18-38
10%	250	25	18-38	14-29	9-19
Mean household size includes case.					
Secondary attack rate 18-38%, secondary cases presented as a range based on these high and low bounds.³⁰⁻³²					

Incidence Density

Using time-specific variables such as date of enrollment, weekly symptom diaries and questionnaires, Incidence Density (ID) will be calculated, defined with the following formula:

Incidence Density =

Number of participants that successfully initiate antiviral therapy within 48 hours of symptom onset (among participants who have a cough and self-test positive for influenza)

Total person-days

Model

The proportion of individuals that 1) test positive and 2) receive and initiate treatment within 48 hours of symptom onset using home-based self-test and delivery methods will be analyzed with a binomial regression GLMM with a log link. The outcome follows a binomial distribution, with the number of successes in a series of n independent Bernoulli trials, where each trial has probability of success p . Successes here are defined as an individual successfully initiated on antiviral therapy within 48 hours of symptom onset using home-based self-test to diagnose influenza and home delivery of antivirals. The model is defined below:

Incidence proportions of influenza will be presented in tables.

A formal statistical comparisons between study periods (control vs. intervention) will be performed using a Wald test of the hypothesis

$H_0: RR=1$

$H_a: RR \neq 1$

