The general form of the model (in matrix notation) is:

$$\mathbf{y} = \log\left(\frac{p}{1-p}\right) = \mathbf{X}\boldsymbol{\beta} + \mathbf{Z}\mathbf{u} + \boldsymbol{\epsilon}$$

Variable	Definition
\mathbf{y}	$N \times 1$ column vector, the outcome variable
\mathbf{X}	$N \times p$ matrix of the p predictor variables
$\boldsymbol{\beta}$	$p \times 1$ column vector of the fixed-effects regression coefficients (the β s)
\mathbf{Z}	$N \times q$ design matrix for the q random effects (the random complement to the fixed \mathbf{X})
\mathbf{u}	$q \times 1$ vector of the random effects (the random complement to the fixed $\boldsymbol{\beta}$)
$\boldsymbol{\epsilon}$	$N \times 1$ column vector of the residuals, that part of \mathbf{y} that is not explained by the model height

where each individual β value represents the change in log-odds of receiving and initiating treatment within 48 hours, that are associated with a particular demographic or clinical risk factor. A one-sided test with $\alpha = .05$ will be used. A table of the estimated Risk Ratios for a one unit increase in each covariate, given the other covariate values will be presented, along with the corresponding 95% confidence intervals, and p-values.

Data cleaning and analysis

All analyses will be performed in R version 3.6.1 using the package 'lme4.'

Secondary Analyses:

Question: How well does the self-test perform in comparison to the gold standard molecular test?

Sensitivity, specificity, PPV and NPV of the self-test will be calculated and compared to the gold standard molecular test. Table 2 (below) presents relevant formulas.

Table 2. Sensitivity, Specificity, PPV, and NPV of the Ellume Self-Test, SFS Household Intervention Study, 2019-2020 influenza season

Test Score	The Truth	
	Has Influenza	Does Not Have Influenza
Positive	True Positives (TP) a	False Positives (FP) b
Negative	False Negatives (FN) c	True Negatives (TN) d

$$\text{Sensitivity} = \frac{TP}{TP+FN} = \frac{a}{a+c} \quad \text{Specificity} = \frac{TN}{TN+FP} = \frac{d}{d+b}$$

$$\text{PPV} = \frac{TP}{TP+FP} = \frac{a}{a+b} \quad \text{NPV} = \frac{TN}{TN+FN} = \frac{d}{d+c}$$

Question: What is the association between influenza infection and: (1) influenza strain (by genetic sequencing) and (2) viral kinetics (maximum titer, duration viral RNA detection)?

Sensitivity analysis

Sensitivity analyses will be performed to explore the uniformity of any treatment effects found in the overall analysis.

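### SAP B5 sets 250 households per arm against a reduction in flu incidence without allowing for a drug that is given only after a household already has an ill member, so the stated power cannot be relied on.

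*SAP*

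**What the plan says.** SAP B5 (Power sample size) tabulates the "Number of clusters needed per arm for two-group cluster-randomized trial - Household intervention study", with columns headed "Effect size (% reduction in flu incidence" at 0.30, 0.40 and 0.50. The inputs are: "All calculations above assume an ICC of 0.29, anticipated average (or actual) cluster size of 4, and a 15% transmission rate for flu". It then concludes: "Based on these calculations, an arm size of 250 households should be sufficient to detect a 30% reduction in flu incidence at 90% power".

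SAP B6 (Endpoint Analyses) gives the expected yield of the same enrolment: "Of these, 25% are estimated to have an individual in the household diagnosed with influenza". Its attack-rate table shows 63 primary cases from 250 households and 34-72 secondary cases at mean household size 4, from a secondary attack rate (SAR) of 18-38%. At a 10% household attack rate it shows 25 primary cases.

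The protocol says who receives the drug. A drug-ineligible participant takes the self-test, but "regardless of the result, they will not be able to receive BXM" (II. Study design). A drug-eligible participant is prescribed BXM only after becoming symptomatic and being diagnosed with probable influenza (V, Onset of Symptoms). The same study design section adds: "Once an eligible study participant receives BXM, no additional household members will be eligible to receive BXM".

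**The concern.** B5 sets its required number of clusters directly against all enrolled households. The intervention is treatment of one ill person, with no prophylaxis of contacts. Any effect on other people's influenza must come from reduced onward spread, in households that already have a case. B5 allows neither for the share of households that will have a case nor for the share of cases that onward spread accounts for, and nothing elsewhere in the documents supplies this.

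The SAP's stated purpose includes reducing transmission within households, and B6 plans a Wald test of control against intervention periods. A reader who trusts the 90% could take a null transmission or incidence result as evidence of no effect when the study had little chance of detecting one.

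**Working it through.** **Inputs.** From SAP B5: ICC 0.29, cluster size m = 4, rate p1 = 0.15. From SAP B6: household attack rate 25% (10% as the low value), SAR 18-38%, household size including the case. B5 gives no alpha. B6 has "A one-sided test with" alpha 0.05 beside a two-sided alternative. Two-sided 0.05 is used here because it reproduces the B5 table.

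**Formulas.** With V = p1(1-p1) + p2(1-p2):
- clusters per arm K = (z_α + z_β)² × V / (p1-p2)² × [1+(m-1)×0.29] / m
- power = Φ(|p1-p2|/SE - 1.96), where SE² = V × [1+(m-1)×0.29] / (mK)

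**Reproducing B5.** If the headers are reductions, as labelled, K = 402/214/129 at 80% power and 538/286/172 at 90%; only the 0.50 column matches the printed table. If the headers are the ratio p2/p1, K = 57/84/129 and 76/112/172, which matches all six cells. The columns therefore represent reductions of 70%, 60% and 50%.

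For a true 30% cut (0.15 to 0.105) with 250 households of 4 per arm: SE = √(0.221475 × 1.87/1000) = 0.0204, 0.045/0.0204 = 2.21, power = Φ(0.25) = 60%. That is the starting point for the present issue, not 90%.

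**Reading (a): 15% is transmission to contacts.** Only households with a first case can show transmission: 250 × 0.25 = 62.5, printed as 63, or 25 at a 10% attack rate. Each has 3 contacts, so the design effect is 1 + 2×0.29 = 1.58. For 63 per arm at 15%: SE = √(0.221475 × 1.58/189) = 0.0430, 0.045/0.0430 = 1.05, power = Φ(-0.91) = 18%. The same formula gives:

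| Households with a first case, per arm | Cut | Baseline 15% | SAR 18% | SAR 38% |
|---|---|---|---|---|
| 63 | 30% | 18% | 21% | 48% |
| 63 | 50% | 46% | 54% | 92% |
| 25 | 30% | 10% | 11% | 22% |
| 31.5 (63 split in two) | 30% | 11% | 13% | 27% |

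Keeping m = 4 with 63 clusters gives 20% instead of 18%, so nearly all of the fall from 60% comes from the number of clusters. A one-sided 0.05 test (1.645 for 1.96) gives 27% at 15% and 32-60% at SAR 18-38%. For 90% power and a 30% cut, 606, 490 and 184 households with a first case are needed per arm at 15%, 18% and 38%.

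**Reading (b): 15% is incidence in all members.** Only secondary cases are preventable. At household size 4 they are 34/(63+34) = 35% of cases at SAR 18% and 72/(63+72) = 53% at SAR 38%. The share of secondary cases that must be averted is:
- for a 30% overall cut: 0.30/0.351 = 86% at SAR 18%, 0.30/0.533 = 56% at SAR 38%
- for a 50% overall cut: 0.50/0.351 = 143% (impossible) at SAR 18%, 0.50/0.533 = 94% at SAR 38%

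These inputs imply 97-135 cases among 250 × 4 = 1,000 people, an incidence of 9.7-13.5% rather than 15%. At that matching incidence, averting every secondary case at SAR 18% (0.097 to 0.063) gives SE = √(0.146622 × 1.87/1000) = 0.0166 and power = Φ(0.034/0.0166 - 1.96) = 54% with 250 per arm.

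**The case against.** The strongest objection is that B5 describes a trial that is not being run. The protocol has one cohort of 250 households and no control arm, so 63 per arm is as hypothetical as 250 per arm. No protocol analysis depends on B5, and the later protocol sizes its primary objective by precision. This stands. It is why the remedy is withdrawal and why the consequence is limited.

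Four stronger readings are tempting, and the documents do not support them.
- **The mechanism takes power from 90% to 18%.** Part of that gap is the header error. The loss due to the mechanism is from about 60% to 18%.
- **Counting case-free households is always wrong.** Under reading (b) they belong in the denominator. That reading is plausible, since SAP section C expects 150 events per 1,000 in the control period. The fault is then the size of effect assumed.
- **A 30% overall cut is impossible.** It is demanding but within the arithmetic limit at size 4. If 15% incidence is held with 63 first cases, 150 - 63 = 87 cases are secondary. A 30% cut then needs 45/87 = 52% of them averted, and a 50% cut 75/87 = 86%.
- **Power can be put at a single 10-20%.** That holds only near the 15% baseline. The plan's own SAR gives up to 48% with 63 per arm.

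The SAP also allows up to 1,000 households. At a 25% attack rate that is about 250 case households in total, still not 250 per arm.

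**Conclusion.** The concern holds in a limited form. B5's sufficiency statement ignores that the drug is triggered by a case and given to one person per household. Under reading (a), power for a 30% cut with 63 households per arm is 18% at a 15% baseline and 21-48% at the plan's SAR. With 25 per arm it is about 10-22%. Dividing the single cohort's 63 case households into two groups gives about 11-27%. Under reading (b), the overall cut cannot exceed 35-53% at household size 4. The header error is a separate fault, and correcting the labels would not cure this one.

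The figures assume two-sided 0.05, the B5 ICC applied also among contacts, no dropout, and every first case treated. The last is favourable: a first case who is drug-ineligible or outside the 48-hour window is not treated, so 63 is an upper bound on households whose first case is treated.

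A reader might infer that the primary objective is underpowered. It is not affected: Protocol XI bases its ±0.12 precision on 63 individuals, not on 250 households.

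**What to change.** Withdraw the B5 sentence that 250 households per arm are sufficient, and label household-transmission and incidence results as descriptive.

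If a transmission calculation is kept for a future two-arm study:
- define the outcome as secondary attack among contacts in households with a first case
- use the expected number of such households as the clusters
- multiply the effect by the share of first cases treated
- take the SAR of 18-38% as the baseline, with 15% as a sensitivity value
- state alpha and sidedness, and print the range of power rather than one figure

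The cost is SAP wording and a short recalculation. The stated power falls. No extra enrolment or data are needed.

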Question: Does influenza incidence change when we look at varying testing timepoints (e.g. testing within 24, 48, and 72 hours of symptom onset)?

Details:

A sensitivity analysis will be performed to assess the effect of delayed testing on the intervention effect. The model will be re-run with three subsets of the data: those that were treated within 24, 48, and 72 hours of symptom onset. This will then be further analyzed with a time*age interaction. For example, we might expect that a 13-year-old might have more detectable RNA virus than an older adult at the same time point.

Data cleaning and software

All analyses will be performed in R version 3.6.1 using packages `'lme4'` and `'swCRTdesign'`.

C. Interim Analysis Plan

Original Plan

The DSMB will meet every month to review study progress and other issues as outlined below. In the proposed 6 month study, it is expected that the DSMB will meet X times.

Study progress and validity

At each monthly visit the DSMB will review data on enrollment, adherence of both households and household members, and all protocol violations. The DSMB will also compare the (pooled) observed influenza incidence rate to the (pooled) expected influenza rate to determine if the influenza incidence rate among study participants is at least as great as the incidence rate assumed in the study design, since incidence varies by influenza season. The DSMB will recommend any changes to the study design they believe are needed to ensure study validity.

Expected event rate: 150/1000 pdy in the control period and 120/1000 pdy in the intervention period; 135/1000 pdy overall.

Efficacy monitoring

Baloxavir-resistant influenza strain transmission

Additional testing and sequencing of non-influenza respiratory pathogens will also occur. Baloxavir resistance will be analyzed via interim analyses and monitored for the duration of the study. In the unlikely event that the incidence of the transmission of baloxavir-resistant strains of flu exceeds 20% of study participants, the study will be halted.

Tables and Figures

Table 1a. Sociodemographic characteristics of individual participants, SFS Household Intervention Study, 2019-2020 influenza season

Variable	Full sample n=	Cases only n=
Sociodemographic variables		
Age - median (range)		
Sex		
Male		
Female		
Race		
American Indian or Alaska Native		
Native Hawaiian or other Pacific Islander		
Black or African American		
White		
Multiple Races		
Other		
Prefer not to say		

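### SAP B5 claims 90% power for a 30% reduction in influenza incidence with 250 households per arm; its own inputs give about 60%, and section C expects a smaller effect that B5 does not cover

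*SAP*

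**What the plan says.** SAP B5 gives a table titled "Number of clusters needed per arm for two-group cluster-randomized trial". Its columns are headed "Effect size (% reduction in flu incidence" and run 0.30, 0.40, 0.50. The entries are 57, 84, 129 for 80% power and 76, 112, 172 for 90% power. The footnote reads "All calculations above assume an ICC of 0.29, anticipated average (or actual) cluster size of 4, and a 15% transmission rate for flu", and the conclusion is "Based on these calculations, an arm size of 250 households should be sufficient to detect a 30% reduction in flu incidence at 90% power". B5 states no alpha and no sidedness.

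SAP section C (Study progress and validity) has the DSMB check whether pooled incidence is "at least as great as the incidence rate assumed in the study design", and then gives "Expected event rate: 150/1000 pdy in the control period and 120/1000 pdy in the intervention period; 135/1000 pdy overall". The unit *pdy* is not defined.

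On the test itself, the Model text in SAP B6 states a Wald test between a control and an intervention period with a two-sided alternative, and then says "A one-sided test with $\alpha = .05$ will be used".

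The protocol (Summary; IV, Study size) plans 250 households in total and describes no control group. Protocol XI bases the sample size on the confidence interval for the proportion starting treatment within 48 hours: ±0.12 with 63 confirmed infections.

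**The concern.** Two features of the SAP do not fit the power sentence. First, in the B5 table the number of clusters rises as the labelled reduction rises, from 57 at 0.30 to 129 at 0.50. A larger reduction should need fewer clusters, so the labels cannot be right as printed. Second, section C starts from what looks like the same baseline (150 per 1000 against 15%) but expects a fall to 120, which is (150 − 120)/150 = 20%. B5 has no column for that.

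The SAP's Purpose includes reducing household transmission, and B6 names cumulative incidence of influenza as its endpoint. A reader could therefore take B5 as assurance that the study can detect a moderate effect on incidence. The DSMB, working from section C, would have a different effect in front of it.

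**Working it through.** **Inputs.** From B5: control rate p1 = 0.15, ICC 0.29, cluster size m = 4, 250 households per arm. Equal allocation and no dropout allowance are assumed, since B5 states neither.

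Design effect = 1 + (4 − 1) × 0.29 = 1.87. Design effect / m = 1.87/4 = 0.4675.

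**Formula.** Clusters per arm = (z_α + z_β)² × [p1(1 − p1) + p2(1 − p2)] / (p1 − p2)² × 0.4675. At two-sided 5%, (z_α + z_β)² is 7.849 for 80% power and 10.507 for 90%.

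**Step 1: reproduce the B5 table.** Columns taken as rate ratios, so p2 = 0.15 × column value:

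| Column | p2 | 80% power | 90% power | B5 prints |
|---|---|---|---|---|
| 0.30 | 0.045 | 56.7 → 57 | 76.0 → 76 | 57, 76 |
| 0.40 | 0.060 | 83.3 → 84 | 111.5 → 112 | 84, 112 |
| 0.50 | 0.075 | 128.4 → 129 | 171.9 → 172 | 129, 172 |

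All six cells match. With the columns taken as reductions, as labelled, p2 is 0.105, 0.090 and 0.075:

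| Column | p2 | 80% power | 90% power |
|---|---|---|---|
| 0.30 | 0.105 | 401.3 → 402 | 537.3 → 538 |
| 0.40 | 0.090 | 213.4 → 214 | 285.7 → 286 |
| 0.50 | 0.075 | 128.4 → 129 | 171.9 → 172 |

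Only the 0.50 column agrees, because there a rate ratio and a reduction are the same thing. The 0.30 column of B5 is thus the size for a 70% reduction.

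**Step 2: power for the effect that B5 names.** Effective number per arm = 250 × 4/1.87 = 534.8. For 15% v. 10.5%:

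- standard error = √[(0.1275 + 0.0940)/534.8] = 0.02035
- 0.045/0.02035 = 2.211
- two-sided 5%: Φ(2.211 − 1.960) = 0.60
- one-sided 5%: Φ(2.211 − 1.645) = 0.71

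Ninety per cent power needs 538 households per arm two-sided, or 438 one-sided. If the ICC is ignored altogether, power is about 86% two-sided and 92% one-sided. So 90% is reached only with a one-sided test and no allowance for the clustering that B5 itself assumes.

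**Step 3: the section C rates.** Read as 15% v. 12% in two parallel arms:

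- standard error = √[(0.1275 + 0.1056)/534.8] = 0.02088
- 0.03/0.02088 = 1.437
- two-sided: Φ(1.437 − 1.960) = 0.30
- one-sided: Φ(1.437 − 1.645) = 0.42

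Clusters per arm needed, two-sided: 951 for 80% power and 1,273 for 90%.

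If *pdy* means person-years, a Poisson approximation with the same design effect uses √[(0.15 + 0.12)/534.8] = 0.02247 for one year of follow-up, which gives about 27% power two-sided. Half a year gives about 15%.

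**Step 4: split the gap.** From 90% to about 60% comes from the column labels; from about 60% to about 30% comes from the smaller effect. Each accounts for about 30 points.

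**The case against.** Several objections have force.

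- The effect used for sizing need not equal the effect expected. This stands: a 20% expectation beside a 30% sizing effect is not in itself an arithmetic error, though the SAP should explain it. It does not rescue the 90%, which fails for the 30% reduction on B5's own inputs.
- Section C's benchmark is a check on pooled event accrual (135 per 1000), not a statement of the design effect. This stands. The phrase about incidence assumed in the design does not make 20% the design effect.
- Section C refers to periods and B5 to arms. The SAP also loads a stepped-wedge package and lists serious adverse events by shelter, so some text may come from another plan; that is inference. It stands to this extent: the 30% figure rests on putting period rates into a parallel-arm formula, and on equating B5's transmission rate with 150 per 1000 *pdy*.
- The protocol has no control arm, so nothing turns on the claim. This stands in part. It makes withdrawal the right remedy, but it does not justify leaving the sentence while the SAP keeps an incidence endpoint and a test of control v. intervention periods.

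A reader might infer that power drops from 90% to 30% because the wrong effect was used, or that a null incidence result would be wrongly read as evidence against the intervention. The documents do not support either. The 90% was never valid for a 30% reduction, so half of the drop has another cause. The second inference needs a control comparison that the protocol does not contain.

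**Conclusion.** The power claim in B5 is wrong as written. For the reduction it names, 250 households per arm give about 60% power two-sided (71% one-sided), because the table's columns are rate ratios labelled as reductions. That conclusion uses only B5's inputs and the method that reproduces its table; B5's missing alpha is covered by giving both versions.

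That section C's 20% reduction lies outside the B5 table is also firm: its columns are reductions of 30%, 40% and 50%, or of 70%, 60% and 50%. The figure of about 30% (42% one-sided) for that reduction is conditional on reading 150 and 120 per 1000 as proportions in two parallel arms. The person-year readings give lower power.

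None of this shows that the protocol's primary estimate is too imprecise. Its half-width follows from its stated count: 1.96 × 0.5/√63 = 0.12.

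**What to change.** Withdraw the incidence power claim from SAP B5, state that the study is not powered for influenza incidence, and refer to the precision statement in Protocol XI as the basis for the sample size.

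If a comparative power statement is kept, four changes are needed together:

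1. relabel the B5 columns as rate ratios;
2. use one effect size in B5 and section C;
3. define *pdy*, and say whether the comparison is between arms or periods;
4. print the power with its alpha and sidedness: at 250 households per arm and two-sided 5%, about 60% for a 30% reduction and about 30% for a 20% reduction.

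Changing section C to match a 30% reduction would not be enough by itself, because the 90% would still be wrong.

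The cost is SAP wording. The stated power becomes less favourable; enrolment does not change.
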